1.2 Sterotactic radiation surgery (SRS)

In more recent years, SRS has been shown to be an effective alternative therapy for patients with brain metastases. It is especially useful in patients with progression of disease following WBRT, for whom treatment-related neurotoxicity is a major concern. SRS enables the delivery of a highly focused radiation dose to a small target with rapid fall-off, thereby limiting radiation to the surrounding normal brain tissue. This feature should potentially reduce the likelihood of developing late neurocognitive deficits, an issue that becomes an increasing concern in long-term survivors. SRS has even emerged as a treatment strategy to limit WBRT and has been studied in the setting of brain metastasis. SRS has been investigated in postoperative management of solitary brain metastases. At least a dozen retrospective reports have been published describing the results of adjuvant SRS. The reported 1-year local control rates is variable and has been found to be as low as 35% and as high as 100% [18, 19]. Review of UPMC's institutional experience showed 6-month and 1-year LC of 76% and 76% respectively, which is consistent with most other reports [20].

However, delivery of postoperative SRS is particularly challenging due to the nebulous appearance of the tumor bed after resection. This difficulty of delineating the margins of the resection cavity may be responsible for the rate of local failure (LF) despite the utilization of adjuvant therapy and lead to additional symptomatic brain necrosis. A commonly employed strategy to improve LC with adjuvant SRS is the addition of a margin to account for target uncertainty and microscopic extension of disease. The Stanford University group reported a significant improvement in (LF) rates with the addition of a 2-mm margin (1-year LF: 3% vs. 16%) without an associated increase in toxicity [21]. In contrast, a French group has reported an experience of delivering SRS with a 2-mm margin and reported no improvement in 1-year LC (69% vs. 72%) and an increased rate of severe parenchymal complications [22].

In addition to localizing the tumor bed, another potential negative consequence to the sequence of postoperative SRS is the time course between resection and radiation treatment. Typically SRS is performed several weeks after surgical removal of brain metastases. During this interval, the tumor bed is given additional time and may have a detrimental impact on LC.

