1.3 Pre-operative SRS

For patients who require surgical removal of a brain metastasis, we hypothesize a more sensible strategy to improve LC may be the delivery of pre-operative SRS followed by immediate tumor resection. Pre-operative target delineation is likely to be more accurate and result in fewer marginal misses. Furthermore, this treatment package could be completed more expeditiously by eliminating the prolonged interval from surgery to SRS. In our experience, this interval was approximately 5 weeks. In addition, the same MRI scan could be used for SRS and surgical resection; resulting in cost savings for patients who otherwise would receive two separate MRI scans for treatment. Finally, pre-operative SRS may facilitate better resection margins by the delivery of dose in the radiation penumbra surrounding the tumor. An early study of pre-operative SRS on brain metastases by Stuart Burri et al., 2010 demonstrated actuarial LC of 97.7%, 84.6%, and 64.0% at six, twelve, and twenty four months, respectively [23]. More recently according to the interim analysis from a phase 1 study of pre-operative SRS for brain metastases by the University of Alabama, pre-operative SRS appears safe with low rates of wound complications or acute grade toxicity along with target volume reduction of 39% [24]. We therefore propose a phase II clinical trial to further investigate the efficacy of this novel approach.

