7.2 Sample size and accrual rate

No more than 24 evaluable patients will be treated in the trial. This study of 24 patients will have 80% power to detect a difference in postulated local tumor control of 85% to a known inference local tumor control set at 60% to be excluded, using a 1-sided test with Type I error rate of 0.05 for 6, 12, and 24 months. The sample size was estimated using a non-inferior power analysis for inference of a single proportion compared to a known proportion. Also, an attrition rate of 20% was included into the estimated sample size. Based on previous efforts in recruiting patients at the University of Pittsburgh Cancer Institute, it is anticipated that at least 5 patients per year will be enrolled in the protocol and the accrual will be completed within 5 years. An evaluable patient is defined as one who completes a single fractions of preoperative SRS followed by surgical resection of appropriate brain metastases. Patients who are not evaluable will be replaced.

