7.4.1 Analysis of the Primary Endpoints

Local control rates for 6 months, 12 months, and 24 months will be analyzed with Kaplan-Meier Survival Curves and the Log-Rank Test.

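### One power calculation (85% vs 60%) is attached to 6, 12 and 24 months with no primary time or success rule, and the log-rank test in Section 7.4.1 is not the test that Section 7.2 powers.

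*Combined protocol and SAP*

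**What the plan says.** The sample size paragraph appears in the same words in Sections 4.2.2 and 7.2. It states: "This study of 24 patients will have 80% power to detect a difference in postulated local tumor control of 85" (per cent), with 60% as the value to be excluded, "using a 1-sided test with Type I error rate of 0.05 for 6, 12, and 24 months". On method it says: "The sample size was estimated using a non-inferior power analysis for inference of a single proportion compared to a known proportion". It adds that "an attrition rate of 20% was included into the estimated sample size". It defines evaluability by treatment received: "An evaluable patient is defined as one who completes a single fractions of preoperative SRS followed by surgical resection of appropriate brain metastases". Anyone who falls outside that definition is replaced, and 24 is the maximum.

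The whole of Section 7.4.1 reads: "Local control rates for 6 months, 12 months, and 24 months will be analyzed with Kaplan-Meier Survival Curves and the Log-Rank Test". Section 7.1 describes a single-arm design. Section 2.1 gives the primary outcome a time frame of up to 3 years and no landmark. Section 7.3 adds generalized linear models across dose levels and does not refer to 60%.

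The background offers two sets of local control figures that bear on the choice of time. Section 1.3 reports that an early pre-operative series "demonstrated actuarial LC of 97.7%, 84.6%, and 64.0% at six, twelve, and twenty four months, respectively". Section 1.2 reports, for post-operative SRS, that "institutional experience showed 6-month and 1-year LC of 76% and 76% respectively".

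**The concern.** A power statement belongs to one hypothesis, one test and one decision rule. Here a single calculation is stretched over three times, and the analysis section names a different method.

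Three things are missing:

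- **The deciding time.** Nothing says whether success is judged at 6, 12 or 24 months, at any of them, or at all of them.
- **The criterion.** There is no cut-off count and no confidence-limit criterion. The 60% appears only in the sample size text.
- **The test.** An ordinary log-rank test compares curves between groups, and this trial has only one arm. It could compare subgroups such as dose groups, but that does not test 60%. A one-sample log-rank test would need a reference curve, which is not given, and would test that whole curve rather than 60% at a fixed time.

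If these choices are made after the data are seen, the same results can be reported as success or as failure.

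**Working it through.** **Inputs.** From Section 7.2: p0 = 0.60, p1 = 0.85, one-sided alpha 0.05, power 80%, N = 24, attrition 20%. From Section 1.3: local control of 97.7%, 84.6% and 64.0% at 6, 12 and 24 months.

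**1. Reproducing N.** Normal approximation for one proportion against a fixed value:

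n = [(1.645·√(0.60·0.40) + 0.842·√(0.85·0.15)) / 0.25]² = 19.58, rounded up to 20.

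20 × 1.2 = 24. (Dividing 20 by 0.8 gives 25. An arcsine version gives 18.76, rounded to 19, and 19/0.8 rounds up to 24.) The planned N therefore belongs to one test at one time.

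**2. Exact rule with 24 assessable patients.** The smallest cut-off that keeps alpha at or below 0.05 is 19 of 24:

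- P(X ≥ 19 | 24, 0.60) = 0.040
- P(X ≥ 19 | 24, 0.85) = 0.861

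**3. The same rule at the cited rates.** All 24 are taken as assessable at each time.

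| Time | Cited local control | P(at least 19 of 24) |
|---|---|---|
| 6 months | 97.7% | over 99% |
| 12 months | 84.6% | 84.7% |
| 24 months | 64.0% | 8.7% |

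With complete follow-up the number controlled cannot rise over time. Requiring success at any time is then the 6-month test, and requiring it at all times is the 24-month test. The table therefore also gives the chance of success under those two rules.

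**4. A flat 85%.** If control is 85% at both 6 and 24 months, no local failure occurs between them. The cited series falls by 97.7 − 64.0 = 33.7 percentage points over that interval and is close to 85% only at 12 months.

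**5. After the planned attrition.** 24 × 0.8 = 19.2, so 19 patients remain if the lost 20% are dropped from the proportion.

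| Test, n = 19 | Needs | Alpha | Power at 85% |
|---|---|---|---|
| Exact binomial | 16 | 2.3% | 68% |
| z-test | 15 | 7.0% | 86% |

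Neither row gives 80% power at a true 0.05, so the claim depends on a test that is not named.

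**6. A test that matches the hypothesis.** Take success to mean that the one-sided 95% lower log-log confidence limit of the 12-month Kaplan-Meier estimate exceeds 60%. With complete follow-up, 5 failures of 24 give a limit of 0.614 (success) and 6 give 0.569 (no success), which is the 19-of-24 rule. With no failures the limit is undefined. The simulation below then required at least 6 patients at risk, since 0.05^(1/6) = 0.607 exceeds 0.60 and 0.05^(1/5) = 0.549 does not.

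Simulated with n = 24, constant hazards and deaths censored:

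| Assumed median survival | Power at 85% | Size at 60% |
|---|---|---|
| No deaths | 86% | 4% |
| 12 to 24 months | 64–74% | 3–4% |
| 8 months | 54% | about 4.7% |
| 5 months | 41% | about 7% |

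These survival values are assumptions. The only median survival in the documents is 4–5 months with WBRT (Section 1.1), which is not an estimate for resected patients. Section 4.4 requires only a life expectancy of at least 12 weeks.

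**The case against.** The strongest defence is that N is correct for the stated hypothesis, that power is conditional on 85%, and that a reader could take the three times as three reports of one curve. The first two statements are right. The 9% at 24 months questions whether 85% is plausible there; it does not refute power given 85%. It also assumes full follow-up. The institutional figures are flat from 6 to 12 months (76% and 76%), which softens the criticism of a flat rate over that interval, though not to 24 months. None of this supplies a deciding time or a test against 60%.

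Several stronger readings are tempting and should not be drawn:

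- **Inflated type I error.** A reader might infer 1 − 0.95³ = 14.3% from three tests at 0.05. That assumes independent tests. With complete follow-up these are nested, and the 19-of-24 rule keeps each at 4.0%.
- **Progression would be censored.** Sections 6.2 and 8.2 end participation for worsening disease, or for target-site progression or treatment effect needing repeat surgery or SRS. A reader might infer that local failures will be lost as censored. No section says so, and documented progression would ordinarily be the event. What is missing is a statement of how such cases count.
- **60% is the wrong null.** The institution's 76% at 1 year invites this, but Section 1.2 also cites 1-year rates from 35% to 100%. More justification would help; its absence is not an error.
- **The 20% must all fall after resection.** Evaluability and replacement suggest this, but the text does not say when attrition occurs.

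Choosing the primary time is the sponsor's decision. It is also fair to object that a landmark rule loses power, and can exceed its nominal size, when survival is short. The fix has to deal with that.

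**Conclusion.** The point stands and must be fixed before analysis. One single-proportion calculation is claimed for three times, no time or rule decides success, and the planned primary analysis does not contain the test that was powered. This follows from the text alone.

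Its size is shown by the cited rates: the chance of success is over 99%, 85% or 9% depending on the time chosen, if all 24 patients are assessable and those rates are true. If 19 remain after the planned attrition, power at 85% is 68% with an exact test, or 86% with a z-test whose actual alpha is 7.0%.

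N = 24 is not wrong for one test at one time. The power figures that allow for deaths are illustrations under assumed survival, not findings about this population. The label non-inferior is a minor wording error: no margin is given, and excluding 60% when 85% is expected is a one-sided superiority comparison with a fixed value.

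**What to change.** - **(a) One primary time.** In Sections 4.2.2, 7.2 and 7.4.1, name a single time for the 60% vs 85% hypothesis and remove the three times from the power sentence. Twelve months is where the cited pre-operative series (84.6%) supports 85%.
- **(b) A matching test.** In Section 7.4.1, replace the log-rank test for the primary endpoint with a one-sided 0.05 test of the Kaplan-Meier estimate at that time against 60%. One example is success if the one-sided 95% lower log-log limit exceeds 60%. Specify a scan window around the landmark and a minimum number at risk that applies whether or not failures occur, because the example rule can exceed 5% when few patients remain.
- **(c) Other times.** Report them descriptively with confidence intervals.
- **(d) Power.** Restate it for the chosen test under the sponsor's own stated survival and loss assumptions, including any effect of the minimum number at risk. Say what the 20% attrition covers.
- **(e) Clarification.** State that tumor progression at the target site that ends participation under Section 6.2 or 8.2 counts as a local failure on its date, and say how radiation or treatment effect is classified.
- **(f) Minor.** Replace the non-inferior label with a one-sided test excluding 60%.

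The cost is wording in these sections and no extra patients. The downside is a conditional and less favourable power statement (for the example rule, 64–74% if median survival is 12 to 24 months), and the other two times lose confirmatory status.

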2.5 SUBJECT SELECTION AND ELIGIBILITY

4.1 Selection of subjects

Enrollment is defined as the first day of protocol therapy.

Patients enrolled in this study must have a measurable brain metastasis which is defined as lesions that can be accurately measured in at least one dimension: [longest diameter to be recorded] on the MRI scan. Patients will have no more than 4 distinct lesions within the brain. The target lesion must measure at least 15mm in at least one dimension and no more than 40mm in any dimension.

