7.3 Data analysis

When possible, generalized linear models (subsuming, for example, logistic regression) will be used to combine data from different dose levels. Model assumptions will be checked graphically prior to analysis. If model assumptions are not met the analysis will be primarily descriptive. Baseline description statistics on all evaluable patients will be provided for demographic variables (age, sex, race/ethnicity), Karnofsky performance status, disease stage and status at the time of enrollment and treatment regimens previously used.

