8.2 Stopping criteria

Research subjects will be withdrawn from the study if any one of the following occur:

- 1) Documented neurological worsening following SRS.
- 2) Inability to tolerate SRS prior to surgical resection.
- 3) Multiple seizures following SRS.
- 4) Progression of tumor or radiation/treatment effect at the target site sufficient to necessitate repeat surgical resection or repeat SRS.

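### Only patients who complete resection after SRS are evaluable and all others are replaced, so the natural reading is a local-control test on a set selected after treatment has begun

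*Combined protocol and SAP*

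**What the plan says.** Section 7.2, repeated in 4.2.2, sets the evaluability rule: "An evaluable patient is defined as one who completes a single fractions of preoperative SRS followed by surgical resection of appropriate brain metastases". It continues: "Patients who are not evaluable will be replaced". Neither section separates reasons for missing surgery.

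A patient is already on study by then. Section 4.1 states: "Enrollment is defined as the first day of protocol therapy". Sections 3.5 and 3.7 place resection 1-7 days after SRS. Section 8.2 withdraws patients for neurological worsening or multiple seizures after SRS, and also for this: "Inability to tolerate SRS prior to surgical resection". Section 6.2 ends participation for treatment side effects or worsening disease.

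The test is sized in the same paragraph that caps the trial at 24 evaluable patients. The postulated local-control rate is 85%, and the rate to be ruled out is 60%. The test is specified in these words: "using a 1-sided test with Type I error rate of 0.05 for 6, 12, and 24 months". Section 7.4.1 plans Kaplan-Meier curves and a log-rank test and names no population. The only set named for any analysis in section 7 is in 7.3: "Baseline description statistics on all evaluable patients will be provided".

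Section 8.3 counts a DLT from the start of radiotherapy over 60 days, with no evaluability condition, and the Protocol Summary has all toxicity recorded. No DLT rate, denominator or boundary is given.

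**The concern.** Whether a patient belongs to the group of 24 is settled after SRS, by whether resection was completed. The third trigger quoted from 8.2 can arise only between SRS and surgery, so the plan itself expects that some irradiated patients may stop there. Such a patient is enrolled and irradiated, is not evaluable, and gives up the place to someone who got through the interval.

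That interval is what distinguishes this sequence from postoperative SRS, and the primary objective concerns patients still awaiting resection. A result limited to those who complete surgery does not show how often the strategy, once begun, ends in resection with local control. With 24 patients, one or two people left out can change the conclusion. If the population is not fixed in advance, it can also be chosen after the results are known.

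**Working it through.** **Inputs from the documents (7.2).** p0 = 0.60, p1 = 0.85, one-sided alpha = 0.05, power 0.80, attrition 20%, N = 24 evaluable.

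**Reproducing N.** One-sample proportion, normal approximation:

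n = [(1.645 × √(0.60 × 0.40) + 0.842 × √(0.85 × 0.15)) / 0.25]² = 19.58, rounded up to 20.

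With attrition, 20 × 1.2 = 24 or 20/0.8 = 25. The stated 24 is reproduced.

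**Pass mark at 24.** The plan gives none, so I take the exact binomial. The smallest count with P(X ≥ r | n = 24, p = 0.60) ≤ 0.05 is r = 19. Its alpha is 0.040, and its power at 0.85 is 0.861. This is the single-proportion test that the sample-size paragraph describes; it treats local-control status as known for all 24.

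**Returning unresected patients.** Assumption: k irradiated patients missed surgery through toxicity or worsening, and each counts as a failure of the strategy. The documents give no value for k, so a range is shown. p = P(X ≥ x | n = 24 + k, p = 0.60).

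| k | n | 19 controlled | 20 controlled |
|---|---|---|---|
| 0 | 24 | 79.2%, p = 0.040 | 83.3%, p = 0.013 |
| 1 | 25 | 76.0%, p = 0.074 | 80.0%, p = 0.029 |
| 2 | 26 | 73.1%, p = 0.122 | 76.9%, p = 0.056 |
| 3 | 27 | 70.4%, p = 0.184 | 74.1%, p = 0.095 |

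A just-passing result is lost with one such patient, and 20/24 is lost with two.

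**Chance of a misleading pass.** Assumption: the true strategy-success rate in all irradiated patients is 60%, and a fraction f is lost before surgery. The rate among evaluable patients is then 0.60/(1 − f), and the rule of at least 19/24 passes as follows.

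| f | Evaluable rate | P(pass) |
|---|---|---|
| 5% | 0.632 | 0.075 |
| 10% | 0.667 | 0.138 |
| 20% | 0.750 | 0.422 |

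The nominal level is 0.05.

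**Power if the test were moved to all irradiated patients.** Take f = 10% and 85% control among evaluable patients. Strategy success is 0.85 × 0.90 = 76.5%, and about 24/0.90 = 26.7, or 27, patients are irradiated. The exact rule at 27 is at least 21 (alpha 0.042), with power of about 54% at 76.5%.

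**The case against.** A reader might go further than the text in three ways.

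- **That harm after SRS makes a patient non-evaluable.** It does not; missing resection does. A patient who seizes or worsens and is still operated on meets the definition in 7.2. Section 8.2 would withdraw that patient but does not say surgery is withheld. How the two sections fit together is unclear.
- **That the DLT rate loses the events before surgery.** Section 8.3 has no evaluability condition, all toxicity is recorded, and section 8.1 provides monthly toxicity review. The safety denominator is unstated, not truncated, so no DLT rate can be called the one the plan would report.
- **That an unresected patient is a local failure.** Section 2.1 measures local control by tumor volume. Missing surgery may be a competing event, and under Kaplan-Meier an early-censored patient may barely move the curve. The figures in the working concern a composite of completion and control, which the plan does not use.

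The defence can add that 7.4.1 names no population, so an evaluable-only analysis is an inference. It can also say that 60% and 85% were set for local control, so making strategy success the tested endpoint would change the design and, on the example above, cost power.

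These points limit the claim and the remedy, but they do not remove the selection rule. Replacement regardless of cause is written down, the test is sized on the set it produces, and nothing says how an irradiated, unresected patient is counted.

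**Conclusion.** The concern holds in this limited form. The 24-patient set on which the 85%-versus-60% test is sized depends on an event after treatment starts, and replacement ignores the cause. On the natural reading, the local-control result omits irradiated patients who do not reach surgery.

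The effect can be decisive at this size: one such patient moves 19/24 from p = 0.040 to p = 0.074, and two move 20/24 from p = 0.013 to p = 0.056. This rests on three assumptions: that such losses occur, at a rate the documents do not give; that they count as strategy failures; and that the exact single-proportion test is used. For safety, the finding is only that the denominator is undefined.

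**What to change.** In 4.2.2, 7.2 and 7.3:

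- (a) Define the safety/DLT set as every patient who receives any SRS.
- (b) Keep every irradiated patient in an all-irradiated analysis, even if replaced for the evaluable count.
- (c) Report the number of non-resections and the reasons. Report also the proportion of all irradiated patients who complete SRS plus resection with local control. Label this strategy success, keep it separate from volume-based local control, and show it beside the evaluable-only result.
- (d) State how unresected patients enter the Kaplan-Meier local-control analysis, for example as a competing event. Reconcile withdrawal under 8.2 with the evaluability definition for patients who worsen but are still resected.

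**Cost.** The change is mainly wording, and the target of 24 evaluable patients stays. Withdrawn irradiated patients need enough continued observation to cover the 60-day DLT window and to be classified for (c), whereas the schedule in 6.3 assumes surgery took place. The reported rate may be less favourable. The 80% power applies only to the evaluable-set test, so strategy success should be presented as an estimate with a confidence interval, not as a replacement for that test.
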